2.3.1. Risk Assessment

Potential Risk of Clinical Significance	Summary of Data/Rationale for Risk	Mitigation Strategy
Study Intervention: GSK3640254		
Prolongation of QT interval	
Preclinically, GSK3640254 inhibited cardiac hERG/IKr potassium, cardiac SCN5A sodium and L-type calcium channel currents recorded from HEK 293 cells stably transfected with complementary Deoxyribonucleic acid (DNA) from the ion channels. In a single-dose safety pharmacology study in telemeterized dogs, increases in QT interval (up to 20 ms) occurred primarily in 1 dog given 17 mg/kg. Later, there were no GSK3640254-related effects on ECG parameters in dogs given up to 25 mg/kg/day for 4 weeks.
 
In the first time in human Study 207187, no participant exhibited corrected QT interval (QTc) change from Baseline >60 ms or QTc >500 ms. In the concentration- QTc analysis, a QT duration corrected for heart rate by Fridericia's formula (QTcF) effect above 10 ms could be excluded for GSK3640254 plasma concentrations of up to approximately 2000 ng/mL (corresponding to doses approximately ≤200 mg QD).
	
 • Protocol exclusion criteria based on Screening ECG parameters and cardiac medical history. • Participants will have ECG monitoring during the course of the study with QTc stopping criteria.

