5.2.1. Definition of endpoint(s)

- AUC(0-inf), AUC(0-t), C_{max}, t_{max} and t_{1/2} of parent and total drug-related material (radioactivity) in plasma.
- Volume of distribution at steady-state (V_{ss}) and clearance (CL) of parent after IV dose (Period 1 only)
- Renal clearance of parent (CL_r) after IV and oral administration
- Oral Clearance (CL/F) and apparent volume of distribution (V_z/F) for the parent following oral administration
- Direct evaluation of absolute bioavailability (F), indirect calculation of fraction of drug escaping first pass hepatic clearance (F_h), fraction absorbed (F_a) and fraction of drug escaping gut metabolism (F_g)
- Urinary and fecal cumulative excretion of total radioactivity as a percentage of the total radioactive dose (Period 1 and Period 2)

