ML(iv)	
Metabolite load following intravenous administration, calculated as:
 $ML(iv) = \frac{[\text{Total Radioactivity AUC}(0 - \infty) - [^{14}\text{C}]GSK3640254 \text{ AUC}(0 - \infty)]}{\text{Total Radioactivity AUC}(0 - \infty)}$ 
Treatment Period 1

ML(po)	
Metabolite load following oral administration, calculated as:
 $ML(po) = \frac{[\text{Total Radioactivity AUC}(0 - \infty) - GSK3640254 \text{ AUC}(0 - \infty)]}{\text{Total Radioactivity AUC}(0 - \infty)}$ 
Treatment Period 2
 
Note: GSK3640254 AUC(0-∞) may be updated depending on the sample analysis conducted but refers to the parent GSK3640254 from oral dose

Fg	
Fraction metabolized by gut wall as a fraction of the oral dose, calculated as:
 $Fg = 1 - [ML(po) - ML(iv)]$

CONFIDENTIAL

Statistical Analysis Plan 213051

Parameter	Parameter Description
$CL_{h,iv,blood}$	
Hepatic blood clearance, calculated as:
 $CL_{h,iv,blood} = CL_{h,iv,plasma} * \text{blood to plasma ratio}$ 
Where $CL_{h,iv,plasma}$ is the hepatic plasma clearance calculated as:
 $CL_{h,iv,plasma} = CL - CL_r$
E_h	
Hepatic extraction ratio, calculated as:
 $E_H = CL_{h,iv,blood} / Q_h$ 
Where Q_h = hepatic blood flow (literature value of 1660 mL/min, Edginton, 2006)
 
Note: if assumption that hepatic CL accounts for 100% of the clearance (i.e. CL_r is negligible), then $E_h = CL * \text{blood to plasma ratio} * Q_h$

F_h	$F_h = 1 - E_h$
F_a	
Fraction absorbed following an oral dose, calculated as follows
 $F_a = \frac{F(0 - \infty)] / (1 - E_H)}{F_g}$
Dose(iv)	Radiometric IV dose calculated by Covance
Dose(oral)	Radiometric oral dose calculated by Covance
$F(0-\infty)$	
Oral absolute bioavailability based on $AUC(0-\infty)$, calculated as:
 $F(0 - \infty) = \frac{GSK3640254 \text{ AUC}(0 - \infty)(\text{oral})}{\text{Dose}(\text{oral}) \frac{\text{Dose}(\text{iv})}{[14C]GSK3640254 \text{ AUC}(0 - \infty)(\text{iv})}}$ 
Per Subject

CONFIDENTIAL

Statistical Analysis Plan 213051

Parameter	Parameter Description
	Note: Radiometric dose will be used for IV. GSK3640254 AUC(0-∞) (Oral) refers to the parent GSK3640254 from oral dose, but may be updated depending on the sample analysis

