- Lambda_z is the terminal phase rate constant
- The following PK parameters AUC(0-∞), AUC(0-t), %AUC_{ex}, Cmax, t_{max}, t_{1/2}, CL, V_{dss}, V_z/F and CL/F, will be derived in Phoenix and sent to S&P. The radiometric IV and oral doses will be calculated by Covance and sent to S&P. Additional parameters will be derived by S&P including CL_r, ML(iv), ML(po), F_g, E_h, F_h Fa, F(0-∞), F(0-t) and the [¹⁴C]-GSK3640254/total radioactivity ratios.

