5.2.2. Main analytical approach

A primary objective is to determine parent GSK3640254 and total drug-related radioactivity systemic concentrations following a single IV microtracer dose of [¹⁴C]-GSK3640254 (with an oral dose of non-radiolabelled GSK3640254) and oral dose of [¹⁴C]-GSK36402541. To assess this, the plasma PK parameters: AUC(0–inf), AUC(0–t), C_{max}, t_{max} and t_{1/2} of parent and total drug-related material (radioactivity) will be summarized and listed. The volume V_{ss} and clearance (CL) of parent after IV dose (Period 1 only), renal clearance of parent (CL_r) after both IV and oral dose, oral clearance (CL/F) and apparent volume of distribution (V_z/F) for the parent following oral administration will also be summarized and listed.

To assess the absolute oral bioavailability of GSK3640254 absolute oral bioavailability (F), F_h, F_a and F_g will be summarized and listed.

To determine the rate and extent of excretion of total radioactivity in urine and feces and the total recovery of radioactivity, following IV and oral administrations of [¹⁴C]-GSK3640254 the PK parameters: Ae and Fe% will be summarized and listed for urine faeces and total (Urine + Faeces)

Table 6 Statistical methodology specification

The following pharmacokinetic statistical analyses will only be performed if sufficient data is available (i.e. if participants have well defined plasma profiles).

Pharmacokinetic Statistical Analyses (Absolute Bioavailability assessment in Treatment Period 1)
Primary Endpoint / Variables

 AUC(0-t), AUC (0-∞) PK parameters of Plasma GSK3640254 (radiolabeled/non-radiolabeled) from IV and oral dose in Period 1 will be analyzed after log_e transformation (PK parameters should be divided by corresponding dose)
Model Specification

 Will be statistically analyzed using a mixed model (MM) for Period1. Terms fitted in the mixed effect ANOVA model will include: 
 Fixed effect : Treatment (IV dose/Oral dose in Period1) Random Effect : Subject The Kenward and Roger method for approximating the denominator degrees of freedom and correcting for bias in the estimated variance-covariance of the fixed effects will be used. Point estimates for the adjusted means on the loge scale, the mean difference between treatments and associated 90% confidence interval for the contrast (test-reference) will be constructed using the residual variance.

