5.3.1.1. Derived plasma pharmacokinetic parameters

The blood: plasma ratio of total radioactivity will be calculated in period 2 according to the following equation:

Ratio $C_b/C_p = \text{Radioactivity Concentration in blood (C}_b\text{)} / \text{Radioactivity Concentration in plasma (C}_p\text{)}$

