5.3.2. Main analytical approach

The blood: plasma ratio of total radioactivity (C_b/C_p) will be calculated at each time point and will be summarized and reported by Pharmaron.

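### SAP Table 4 multiplies by the blood:plasma ratio where it must divide, which biases the primary endpoints Fh and Fa unless the ratio is 1

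*SAP*

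**What the plan says.** The derivation is in SAP section 5.2.1.2.1, Table 4. Hepatic plasma clearance is CL minus CLr, where CL is the IV dose over the plasma AUC of labelled parent in Period 1. It is converted to a blood clearance by "CL_{h,iv,blood} = CL_{h,iv,plasma} * \text{blood to plasma ratio". Eh is that blood clearance over Qh, described as "hepatic blood flow (literature value of 1660 mL/min". Then Fh = 1 − Eh, and Fa = F/(1 − Eh)/Fg.

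The ratio is defined only under the secondary endpoint. Section 5.3.1.1 states: "The blood: plasma ratio of total radioactivity will be calculated in period 2 according to the following equation", and the equation there is radioactivity concentration in blood (Cb) over that in plasma (Cp). Section 5.3.2 adds: "The blood: plasma ratio of total radioactivity (C_b/C_p) will be calculated at each time point".

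Fh and Fa are primary endpoints. SAP section 5.2.1 lists "Direct evaluation of absolute bioavailability (F), indirect calculation of fraction of drug escaping first pass hepatic clearance", followed by Fa and Fg, and section 5.2.2 has all of them summarised and listed. The Table 4 notes assign the calculation: "Additional parameters will be derived by S&P including" Eh, Fh and Fa.

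**The concern.** Cb/Cp carries a plasma clearance to a blood clearance by division. Multiplication would be right only for the inverse ratio, Cp/Cb, and neither document defines or names that. The conversion cannot be skipped, because CL is measured in plasma and Qh is a blood flow.

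The wrong operator passes through Eh into Fh and Fa. The product Fa × Fh = F/Fg does not change, so the error moves part of the bioavailability loss between hepatic first pass and absorption, which is the split these two endpoints are meant to estimate. The results can still look reasonable: in the 100 mL/min example below, Fh comes out as 0.964 instead of 0.900.

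Table 4 also does not say which ratio it takes. The one defined is for total radioactivity in Period 2 and has a value at each time point, whereas CL is for parent drug in Period 1. No single value is named.

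**Working it through.** The SAP states no value for Eh, Fh or Fa, so there is no printed figure to reproduce. The check is on the formula.

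**Inputs.** From SAP Table 4: Qh = 1660 mL/min, Eh = CLh,blood/Qh, Fh = 1 − Eh, Fa = F/(Fh × Fg). From SAP 5.3.1.1: R = Cb/Cp. Assumed, because the documents give neither: hepatic plasma clearance CL of 20–200 mL/min and R of 0.6–1.5.

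**Direction.** The elimination rate is CLp × Cp = CLb × Cb, so CLb = CLp/R. Numerical check with CLp = 200, Cp = 10, R = 0.6, hence Cb = 6:

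- True rate: 200 × 10 = 2000.
- Dividing: (200/0.6) × 6 = 2000.
- As printed: (200 × 0.6) × 6 = 720.

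Only division conserves the rate.

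**Effect on Eh.** Printed Eh/correct Eh = (CL × R/Qh)/(CL/(R × Qh)) = R². This is 0.36 at R = 0.6, 0.64 at 0.8, 1 at 1.0, 1.44 at 1.2 and 2.25 at 1.5. It assumes that the ratio entered equals the parent ratio.

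**Effect on Fa.** Printed Fa/correct Fa = [1 − CL/(R × 1660)]/[1 − CL × R/1660]. Example at CL = 100 and R = 0.6: correct Eh = 100/(0.6 × 1660) = 0.1004 and printed Eh = 100 × 0.6/1660 = 0.0361. The Fa ratio is then 0.8996/0.9639 = 0.933.

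| Assumed CL (mL/min) | R 0.6 | R 0.8 | R 1.2 | R 1.5 |
|---|---|---|---|---|
| 20 | −1.3% | −0.6% | +0.5% | +1.0% |
| 50 | −3.3% | −1.4% | +1.2% | +2.6% |
| 100 | −6.7% | −2.9% | +2.4% | +5.5% |
| 200 | −13.9% | −6.0% | +5.2% | +12.3% |

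For R below 1, Fh is overstated and Fa understated; above 1 the reverse.

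**Which CL is plausible.** The documents limit it only loosely. Protocol 2.3.1 links "plasma concentrations of up to approximately 2000 ng/mL" to doses of about 200 mg once daily or less. Assume, since no mean is reported, an average of 1000–2000 ng/mL at 200 mg daily. Then CL/F = (200 mg/1440 min)/Cavg:

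- 2000 ng/mL gives 69.4 mL/min.
- 1000 ng/mL gives 138.9 mL/min.

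With the 15% oral bioavailability used for planning in Protocol 4.3, CL = 0.15 × 69.4 to 0.15 × 138.9 = 10.4 to 20.8 mL/min. Treating all of this as hepatic, the Fa error is 0.2–0.6% in size at R = 0.8 or 1.2, and 0.5–1.3% at R = 0.6 or 1.5.

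The opposite extreme is Fa × Fg = 1, so that F = Fh = 1/(1 + a) with a = (CL/F)/(R × 1660). At CL/F = 138.9 the Fa ratio is 0.918 at R = 0.6 and 1.075 at R = 1.5, an error of at most about 8%.

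Lower concentrations cannot be excluded. Protocol 4.3 puts the 200 mg single-dose Cmax in healthy participants more than 200-fold above about 3 ng/mL, that is above about 600 ng/mL. If the average were 500–600 ng/mL, CL/F would be 231–278 mL/min. In the same extreme case the Fa ratio is then 0.871 to 0.849 at R = 0.6 and 1.132 to 1.162 at R = 1.5, an error of 13–16%.

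**The case against.** The strongest objection concerns size and consequence, not the algebra. At the only bioavailability the protocol states, the Fa error is about 1% or less in most of the range: with CL = 20.8, R = 0.6 and Fg = 1, Fa would be 0.151 instead of 0.153. The range of R is assumed. Against a CL/F of 69–139 mL/min, a CL of 200 mL/min would require F above 100%, so that row of the table applies only if concentrations are lower than assumed. The study is descriptive, with four to six participants, and no decision depends on Fh or Fa. Both can be recomputed from CL, CLr and the reported ratio. All of this stands, and it limits the importance of the point. It does not make the printed formula right, and 15% is described as a conservative planning value.

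A second objection is that the text was read from PDF and the layout of Table 4 is damaged. The note for negligible CLr, for example, prints multiplication by Qh where the Eh line divides. That note should be checked against the PDF and is given no weight here. The line at issue prints a clear multiplication sign, and the Eh line below it prints a proper division sign, so misreading is unlikely. Checking both lines costs nothing.

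Third, Protocol 4.3 reports parent drug as the predominant component in human plasma, which supports total radioactivity as a proxy for the parent ratio. The rule for reducing time points to one value may sit in the Output and Programming Specification, which is not available here. That softens the question of which ratio is used to a request for detail. It does not touch the operator.

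**Conclusion.** The point holds. With the ratio defined as Cb/Cp, Table 4 must divide, and nothing elsewhere in the SAP or protocol corrects it. Followed as written, the plan gives wrong values of Eh, Fh and Fa whenever the ratio differs from 1. The factor of R² on Eh is algebraic and needs only that the ratio used equals the parent ratio. The resulting bias in Fh and Fa cannot be fixed from the documents: probably small if bioavailability is near 15%, potentially of the order of 10% if bioavailability is high and R is far from 1. Direct F, Fg, plasma CL and the excretion endpoints are unaffected. It should be corrected because it is the stated derivation of named primary endpoints, but it does not threaten the study's other conclusions.

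**What to change.** - In Table 4, write CLh,iv,blood = CLh,iv,plasma/(Cb/Cp).
- For negligible CLr, write Eh = CL/[(Cb/Cp) × Qh], after checking the printed note against the original PDF.
- State which ratio enters Table 4: analyte, period, and how one value is taken from the time-point ratios. If it is the Period 2 total-radioactivity ratio, say that it stands in for the parent ratio.
- Optionally, add one test case to the programming specification: hepatic plasma clearance 100 mL/min, Cb/Cp 0.6 and Qh 1660 mL/min must return Eh 0.100 and Fh 0.900. The printed formula returns 0.036 and 0.964.

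The cost is one changed operator, one note to check, one sentence and, if wanted, one test case. No new samples or data are needed.

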GlaxoSmithKline have provided experimental data on the biokinetics of [¹⁴C]GSK3640254 mesylate following its oral administration to pigmented and albino rats. The data have been used to determine the likely dose to male volunteers from a single administration of the radio-labelled compound. The assumption is made that the levels of uptake and retention by tissues will be the same in man as in the experimental animals. Committed equivalent doses to tissues and organs and committed effective dose (E(50)) have been calculated according to the 1990 Recommendations of the International Commission on Radiological Protection (ICRP)¹ as implemented in the Ionising Radiations Regulations 1999² in response to EU Council Directive 96/29/Euratom³. ICRP Publication 105⁴ recommends the use of dose constraints, where the exposure of volunteers in biomedical research provides no direct benefit to them, to limit any inequity between individual risk and societal benefit and because there is no specific further protection in the form of a dose limit. The E(50) can be compared with the dose categories proposed for research projects involving human volunteers by the World Health Organization (WHO)⁵ and ICRP⁶.

2. Data used in calculations

Results were provided for the urinary and faecal excretion of ¹⁴C following the oral administration of [¹⁴C]GSK3640254 mesylate to albino rats. Expressed as percentages of total excretion, the values used for the calculations were 0.04% urinary and 99.96% faecal excretion.

Data were provided for the tissue distribution of ¹⁴C after oral administration of [¹⁴C]GSK3640254 mesylate to pigmented rats. Concentrations of radio-labelled compound retained in the tissues were expressed as nanogram equivalents per gram (ng eq/g) of tissue. These concentrations were converted to values for the percentage of administered activity retained in individual tissues or organs using standard organ weights⁷. Doses were calculated using values for 21 tissues at 5 time-points between 1 and 240 hours after administration. Retention half-time data were provided for the eye on the basis of measurements in pigmented rats; a half-time of 23.2 hours was estimated.

3. Method of calculation

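### SAP Table 4: the Note giving Eh when renal clearance is negligible multiplies by hepatic blood flow where the row's own formula divides, so Fh and Fa are invalid if the Note is applied as printed

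*SAP*

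**What the plan says.** The Eh row of SAP Table 4 (section 5.2.1.2.1) contains two formulas.

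- **Main formula:** "E_H = CL_{h,iv,blood} / Q_h", with Qh a "literature value of 1660 mL/min". The row above obtains hepatic plasma clearance as "CL_{h,iv,plasma} = CL - CL_r" and multiplies it by the blood:plasma ratio to get hepatic blood clearance.
- **Note:** "Note: if assumption that hepatic CL accounts for 100% of the clearance", which the SAP glosses as CLr being negligible, "then $E_h = CL * \text{blood to plasma ratio} * Q_h".

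The next rows set Fh = 1 − Eh and Fa = [F/(1 − Eh)]/Fg, so both inherit whatever Eh is used. SAP 1.2.1 and 5.2.1 list Fh and Fa, with F and Fg, under the primary objective on absolute bioavailability. The notes to Table 4 assign Eh, Fh and Fa to S&P for derivation. Protocol 9.4.3 gives no formula for Fh or Fa, so Table 4 is their only definition in these two documents. The SAP sets no threshold for calling CLr negligible and states no unit for CL in Table 4.

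**The concern.** An extraction ratio is a clearance divided by a flow, and lies between 0 and 1. The Note is meant as a special case of the formula above it, but it changes the operator on Qh from division to multiplication. The result is a flow squared.

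An analyst who judges CLr negligible and codes the Note as printed would get an Eh that is not a fraction, and then an Fh and an Fa with no meaning. The outcome depends on the working unit. In the SAP's mL/min the answer is visibly absurd. In L/min it can fall between 0 and 1 and be reported without question.

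**Working it through.** The plan states no numerical value of Eh, so there is no figure to reproduce. The check is whether the two formulas agree where they should.

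**Inputs from the SAP:** Qh = 1660 mL/min; hepatic plasma clearance = CL − CLr; hepatic blood clearance = hepatic plasma clearance × R, where R is the blood:plasma ratio.

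**Assumed inputs (not in the documents):** CL 10 to 1000 mL/min; R 0.55 to 1.0; for the Fa illustration, F = 0.30 and Fg = 1.

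**Step 1, algebra.** Set CLr = 0.

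- Main formula: Eh = CL × R / Qh, which is dimensionless.
- Note: Eh = CL × R × Qh, in units of flow squared.
- Note divided by main formula: Qh², whatever CL and R are.

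**Step 2, the SAP's unit (mL/min).** The factor is 1660² = 2,755,600. Take CL = 50 and R = 0.7.

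- Note: Eh = 50 × 0.7 × 1660 = 58,100; Fh = 1 − 58,100 = −58,099; Fa = 0.30 / (−58,099) = −0.000005.
- Division: Eh = 50 × 0.7 / 1660 = 0.021; Fh = 0.979; Fa = 0.30 / 0.979 = 0.306.

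Over the whole assumed range the Note gives Eh from 10 × 0.55 × 1660 = 9,130 to 1000 × 1.0 × 1660 = 1,660,000. Division gives 0.003 to 0.60. The Note could return a value of 1 or less only if CL × R were at most 1/1660 = 0.0006 mL/min.

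**Step 3, other units, same participant.**

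| Unit | CL | Qh | Note | Division | Factor (Qh²) |
|---|---|---|---|---|---|
| mL/min | 50 | 1660 | 58,100 | 0.021 | 2,755,600 |
| L/h | 3 | 99.6 | 209 | 0.021 | 9,920 |
| L/min | 0.05 | 1.66 | 0.058 | 0.021 | 2.76 |

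Division gives the same answer in every unit; the Note does not. In L/min the Note stays at or below 1 whenever CL × R is at most 1/1.66 = 0.60 L/min. For example, with CL = 0.3 L/min and R = 1.0 the Note gives 0.3 × 1.66 = 0.498, against 0.3 / 1.66 = 0.181. Fh is then 0.502 instead of 0.819, and Fa is too high by 0.819 / 0.502 = 1.63. A range check would pass this.

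**Step 4, is the shortcut needed?** If CLr were 5% of a CL of 50 mL/min, the main formula gives 47.5 × 0.7 / 1660 = 0.0200, against 0.0211 with CLr ignored. The main formula handles a small CLr directly.

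The division figures use the SAP's own multiplication by R. Whether that is the right plasma-to-blood conversion is a separate question. Dividing by R would give 50 / 0.7 / 1660 = 0.043 in the first example. The Qh error is present either way.

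**The case against.** The best defence is that the correct formula stands in the same row. CLr is a planned parameter, derived by the same group, and entering a near-zero CLr in the main formula gives the intended Eh without the Note. The Note is worded as an optional simplification and looks like a slip of one character. In mL/min the result would be hard to miss. All of that stands, and it limits the consequence. It does not make the printed formula right.

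A reader might go further than the documents allow in two ways.

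- **That this drug will probably follow the negligible-CLr branch.** The only support is Protocol Appendix 6, where "the values used for the calculations were 0.04% urinary and 99.96% faecal excretion". Those are orally dosed rats, total radioactivity, and shares of total excretion. Faecal activity after an oral dose can include drug never absorbed. The appendix's assumption that all faecal activity arrived through bile serves the dosimetry and is not a finding. No human CLr is given.
- **That analysts would be forced to depart from the SAP on a primary endpoint after seeing data.** Using the main formula is not a departure. It is a choice between two SAP statements, one of them dimensionally impossible. The study is descriptive with no hypothesis test, and the choice does not depend on the results.

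A reader may also suspect a typesetting fault, since the Fa expression nearby has an unmatched bracket. That cannot be fully excluded, but the division by Qh just above is intact and the Note carries two explicit multiplication signs.

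**Conclusion.** Wrong as written. The Note contradicts the main formula in its own row and cannot yield an extraction ratio. This follows from the printed formulas alone and needs no assumption about CL or the blood:plasma ratio.

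The consequence is conditional. If the Note is applied literally, Eh is wrong by Qh squared: about 2.8 million in mL/min and 2.76 in L/min. The larger figure should not be quoted as though it held in every unit. Fh and Fa are invalid in that case, but not if the main formula is used. Whether the Note's branch will be used is not established by the documents. F, the Period 1 bioavailability model, CL, AUC, Fg and recovery of radioactivity do not depend on Eh. The numerical examples rest on assumed CL, R, F and Fg.

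**What to change.** Do one of the following in SAP Table 4 before parameters are derived.

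- Change the Note to Eh = CLblood / Qh, where CLblood is total blood clearance obtained with the same plasma-to-blood conversion as the main formula.
- Delete the Note and use the main formula throughout, with CLr as estimated.

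State that CL and Qh must be in the same unit (mL/min, to match the 1660 value). Add a programming check that Eh lies between 0 and 1 before Fh and Fa are computed, as a secondary safeguard only: it would not catch the L/min case.

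The cost is a one-line SAP correction plus a sentence on units. Design, sampling and participants are not affected.
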